Dexamethasone Administration To Improve Patient Recovery In Ambulatory Vaginal Reconstructive Surgery: Is There A Role?

Investigators: [name], [name], [name], [name], [name], [name], G [name].

Primary Investigator: Dr G [name]

Introduction:

The lifetime risk of undergoing surgical intervention for pelvic organ prolapse (POP) is estimated to be 10% and it is projected that from 2010 to 2050, the number of surgeries for POP will rise by 47.2%, from 166,000 to 245,970.¹ In 1980, accounting for the rising costs of health care, congress approved Medicare to reimburse procedures performed at outpatient and ambulatory surgery centers.² This led to an increasing number of stress incontinence (SUI) procedures being performed in the ambulatory setting from 34,968 in 1996 to 105,656 in 2006.³ However, the number of ambulatory POP surgeries decreased in the same time period. This was possibly due to the increase in the mean age of women undergoing ambulatory procedures for POP and SUI during that time periods.

Our institution has performed outpatient surgeries for POP and SUI for the past 3 years. Patients have tolerated same day surgery with minimal complications. In our previous prospective study assessing satisfaction after outpatient surgeries for POP and SUI, patients had a decreased quality of recovery at 48 hours compared to baseline.⁴ We also recognized that nausea and pain control could have been better addressed. Unpleasant postoperative nausea and vomiting, pain control, return to normal voiding and return of bowel function can influence the quality of recovery (QOR) from surgery.⁵ Postoperative nausea and vomiting (PONV) and pain management are particularly troubling for the patients. This might also delay discharge and prolong convalescence from the surgery.

Subjects will be selected to participate based on inclusion and exclusion criteria. All subjects meeting inclusion criteria will be scheduled for surgery with one of the urogynecologists. Consent will be done prior to the day of surgery, but subjects will be allowed to sign the consent form the day of surgery if they had a discussion about participating in the research prior and were given time to consider participation.

Inclusion Criteria:

1. Women over the age of 18
2. Women scheduled for vaginal POP reconstructive surgery with or without concomitant anti-incontinence procedure and with or without hysterectomy
3. ASA class 1-2

Exclusion Criteria:

1. Daily use of steroids, antiemetics in the month prior to surgery
2. Chronic pain requiring daily opioid treatment
3. History of allergy/intolerance to Dexamethasone
4. ASA class 3
5. Numerical Pain score of more than 4 at baseline
6. Renal/Liver disease
7. Diabetes mellitus

Dexamethasone Vaginal Surgery

Version 1

3/9/2017

8. Pregnancy
9. Inability to answer questionnaires
10. Any systemic infections
11. Immuno compromised status
12. Patients with planned overnight stay

Randomization:

All subjects will be assigned a number at the time of enrollment. Patient will be randomized to receive either Dexamethasone 8 mg or Normal saline at the time of anesthesia induction. A computer generated table will assign these subjects into two groups. The patients will be blinded to the group assignment. The envelope containing the group allotment will be opened in the operating room at the time of induction. However, the Anesthesiologist and surgeon will not be blinded to the group allotment. Dexamethasone 8mg or normal saline will be mixed and administered at the time of induction.

Preoperatively:

Prior to the surgery, patients will be asked to complete a numerical pain scale (NPS) for pain from 0 to 10 cm and the QoR 40.

All subjects will undergo urodynamics prior to surgery to detect baseline voiding function and SUI.

Anesthesia:

Subjects undergoing general anesthesia and will receive propofol induction, in combination with a muscle relaxant and inhalational gas per anesthesia standard of care at our institution. A maximum of 200 mcg of Fentanyl will be used for each patient during the procedure and immediate postoperative period.

For patients undergoing spinal anesthesia, 0.75% Bupivacaine, 8-12 mg depending on the duration of the surgery and discretion of the anesthesiologist. Patients will also receive propofol infusion at sedation level.

Fluids will be administered by anesthesiology in the usual manner.

Prophylactic antibiotics and Preoperative drugs:

Prophylactic antibiotics such as Ancef, Flagyl and Gentamycin or Vancomycin if Penicillin allergic is to be given prior to incision. Participants will undergo surgery at the Cleveland Clinic Florida by the urogynecology faculty and 3 fellows.

Vaginal packing:

Vaginal packing will be placed after all surgeries as deemed necessary by the surgeon, using gauze. Vaginal packing will be removed at the time of the voiding trial on postoperative day (POD) 0.

Dexamethasone Vaginal Surgery

Version 1

3/9/2017

Postoperative pain management:

Patients will be given IV Morphine (or alternative in case of sensitivities) at doses of 2-4 mg every 10 minutes for moderate to severe pain assessed by a nursing administered pain scale. The maximum dosage administered will be 16 mg. Other alternative medications include IV toradol (30 mg for patients < 60 and 15mg for patients > 60 yrs). Patients may receive oral medications prior to discharge from the PACU. The standard oral medications administered will be Norco, Dilaudid, Tylenol, Percocet and Ultram.

Postoperative antiemetics:

Patients will be given Ondansetron 4mg IV every 8 hours as first line, followed by prochlorperazine 10 mg IV every 6 hours as second line.

Voiding trial:

A voiding trial will be performed on POD 0 once the subjects are able to stand and ambulate to the bathroom. Voiding trial will consist of removing the vaginal packing and back filling the bladder with 300cc of saline or less if the subject has urgency. A voiding trial is considered successful if the subject voids at least 200cc and has a bladder scan showing less than 33% remaining. If a subject is unable to void after an hour, an additional hour will be permitted. However, after 2 hours from when the bladder was backfilled the subject is still unable to void, the Foley will be replaced and the subjects will be discharged home with a Foley catheter, leg bag and leg bag teaching.

The office will call and schedule an office nurse visit to remove the Foley between post-operative day number 5 to 7.

Postoperatively:

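### The anesthesiologist learns the arm at induction, and no rule or record covers non-study steroids or antiemetic prophylaxis during surgery, so co-treatment could differ by arm

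*Combined protocol and SAP*

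**What the plan says.** All references are to the combined protocol and SAP.

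- **Randomization.** The comparison is set out as "Patient will be randomized to receive either Dexamethasone 8 mg or Normal saline at the time of anesthesia induction". The allocation envelope is opened in the operating room as anesthesia is induced. Patients are blinded, but "the Anesthesiologist and surgeon will not be blinded to the group allotment".
- **Exclusion Criteria, item 1.** The only limit on other steroids or antiemetics is an eligibility rule: "Daily use of steroids, antiemetics in the month prior to surgery".
- **Anesthesia.** This section covers the agents for general and spinal anesthesia, a cap on fentanyl, and fluids. It does not mention antiemetic prophylaxis or non-study steroids.
- **Prophylactic antibiotics and Preoperative drugs.** Despite the second half of its title, the only drugs this section names are antibiotics.
- **Postoperative antiemetics.** This section names a two-step regimen, of which the first step reads: "Patients will be given Ondansetron 4mg IV every 8 hours as first line". A second-line drug is also named. The wording is the same for both arms, and it applies only after surgery. The discharge antiemetic (Discharge section) is also the same for both arms.
- **Data Collection.** The items named for the database are demographic and history variables. Co-medication is not among them.

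**The concern.** The person who gives the intraoperative drugs knows which women received saline, and the plan is silent on whether those women may be given something else for nausea. The Introduction says that nausea and pain control at this institution left room for improvement, so a wish to cover a patient known to be on saline is easy to imagine.

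Randomization does not balance co-treatment that is chosen after allocation is known. The background section expects dexamethasone to work through nausea and pain, and the Introduction names both as influences on quality of recovery. Extra treatment given mainly to saline patients would thus act on the same outcomes the trial measures and pull the arms together. A null result could then mean that dexamethasone does not help, or that the controls were treated by another route. Because co-medication is not listed for collection, the plan gives no way to tell these apart afterwards.

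**Working it through.** **1. Does any rule close the gap?** Taking the sections in order of time:

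| Period | Rule on non-study steroids or antiemetics | Arm known to the treating clinician? |
|---|---|---|
| Month before surgery | Daily users excluded | No (before allocation) |
| Arrival to induction | None | No |
| Induction to end of surgery | None | Yes |
| After surgery and at discharge | Named antiemetics, same text for both arms | Surgeon and anesthesiologist: yes |

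The exposed row is the third: the arm is known, there is no rule, and no record is required.

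**2. The plan's own figure.** Sample Size gives 80% power, a difference of 22 points and 22 per group. It gives neither the SD nor alpha, so the 22 can only be solved backwards. I assume two-sided alpha 0.05.

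- Noncentral t: 80% power with 22 per arm needs d = 0.865, so SD = 22 / 0.865 = 25.4.
- Normal approximation: SD = 22 × √(22/2) / (1.960 + 0.842) = 26.0.

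Recruiting 27 per arm adds no reserve if dropout is as planned: 27 × 0.8 = 21.6 evaluable.

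**3. Effect of co-treatment.** Let f be the share of saline patients given a non-study agent, and e its effect as a fraction of dexamethasone's. The expected contrast is 22 × (1 − f × e). In the normal approximation, power = Φ[(1.960 + 0.842) × (1 − f × e) − 1.960]. The SD cancels, so these results depend on the planned 80% and on alpha, but not on the back-solved SD. The noncentral t gives the same percentages.

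Fully effective agent (e = 1):

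| f | Contrast (points) | Argument of Φ | Power |
|---|---|---|---|
| 0 | 22.0 | 2.802 − 1.960 = 0.842 | 80% |
| 10% | 19.8 | 2.521 − 1.960 = 0.561 | 71% |
| 20% | 17.6 | 2.241 − 1.960 = 0.281 | 61% |
| 30% | 15.4 | 1.961 − 1.960 = 0.001 | 50% |

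Half-effective agent (e = 0.5): f = 20% gives f × e = 0.10, which is the 10% row, about 71%.

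**4. Sensitivity to the alpha assumption.** With one-sided alpha 0.05, replace 1.960 by 1.645. The argument becomes 2.487 × (1 − f × e) − 1.645. For e = 1 and f = 10%, 20% and 30% this is 0.593, 0.344 and 0.096, or power of about 72%, 63% and 54%. The pattern is the same.

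The documents give no value for f or e.

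**The case against.** The strongest reply is that no passage shows dilution happening. None describes routine intraoperative prophylaxis at this site or gives a rate, and the antiemetics that are specified, after surgery and at discharge, are worded identically for both arms. That stands, and it limits the claim to a possibility. It does not close the gap, because those rules begin after the period in question.

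A second reply is that the power figures are close to a worst case. That also stands. They assume an agent that matches dexamethasone on total QoR-40, while the background section credits dexamethasone with an effect on pain as well as on nausea. An agent that acts on nausea alone would be expected to do less.

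A third is that the Data Collection list may not be exhaustive and the anesthetic record would show what was given. Perhaps, but the plan does not say that those entries are extracted or compared by arm. The planned multivariate analysis does not help either: it names no co-medication variable, and adjusting for treatment chosen after allocation would not restore the randomized comparison.

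A reader might infer two stronger points that the documents do not support.

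- **That exclusion item 1 is a leaky washout.** It is an eligibility rule and tells no one to stop a drug. Occasional use before surgery precedes the opening of the envelope, so it is balanced between arms in expectation and does not favour saline. Widening the criterion would be a preference about eligibility and would not address this problem.
- **That the standard-of-care wording licenses extra prophylaxis.** The phrase is "in combination with a muscle relaxant and inhalational gas per anesthesia standard of care at our institution". It belongs to a sentence about general-anesthesia agents and says nothing about antiemetics or steroids. The gap comes from silence, not from that sentence.

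**Conclusion.** The point holds as a gap in protection against bias. The anesthesiologist knows the arm from induction, and intraoperative non-study steroids and antiemetic prophylaxis are neither governed nor listed for recording. Co-treatment can therefore depend on the arm. The direction is conditional: use that favours saline patients shrinks the contrasts.

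As an upper bound, power falls from 80% to about 71%, 61% or 50% when 10%, 20% or 30% of saline patients are co-treated. This rests on an assumed two-sided alpha of 0.05, 22 evaluable per arm, an assumed share, and an agent equal to dexamethasone; less effective agents cost proportionately less of the contrast. The change is worth making because it is cheap and must be in place before patients are treated. The figures do not show that the comparison is in fact diluted.

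**What to change.** In Randomization and Anesthesia, add three requirements:

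1. Any planned intraoperative use of a non-study antiemetic or steroid is decided and recorded before the envelope is opened, so that it cannot depend on the arm.
2. Any later use is recorded with its reason.
3. Data Collection includes these items, and Data Analysis reports use by arm.

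Which agents are used, and any treatment a patient clinically needs, remain with the clinicians. Nothing is withheld. Exclusion item 1 can stay as it is.

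The cost is a few sentences of protocol text, one case-report field and one extra step before induction. The sample size does not change.

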QoR is a validated tool that has been used in gynecology surgery. Women in general have a lower QoR with a mean score of 162 postoperatively¹⁰. Based on 80% power to detect a mean difference of 22 points between the two groups in the overall QoR 40, 22 subjects in each group will be needed. Allowing for a dropout rate of 20%, sample size of 54 subjects will be recruited (5 in each group). Therefore each treatment arm will include 27 subjects.

Data Analysis:

Demographic statistics will be compared using student t-test for continuous variables, Wilcoxon Rank Sum test for ordinal or categorical data.

The primary endpoint of change in QoR from baseline will be analyzed through t- test.

Secondary endpoints will be analyzed using t-test for 1) change in QoR-40 score from baseline to POD 1 2) change in QoR-40 from baseline to 6 weeks post-operatively 3) change in QoR-40 from POD1 to 6 weeks post-operatively 3) time to discharge and 4) time to void.

Dexamethasone Vaginal Surgery

Version 1

3/9/2017

Wilcoxon Rank Sum will be used to evaluate postoperative complications including hematoma formation, UTI's, reoperations, readmission, and reinsertion of Foley catheter after discharge.

Univariate and multivariate analysis will be performed to evaluate for confounding variables.

Budget:

No additional funding is required for this study outside of nursing and fellow resources already budgeted into Department of Urogynecology.

4. Alas AN, Espaillet L, Plowright L, Aguilar V, Davila GW. Same-day surgery for pelvic organ prolapse and urinary incontinence: Assessing satisfaction and morbidity. *Perioperative Care and Operating Room Management.*5:20-26.

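### Is recruiting 27 women per arm too few to allow for the stated 20% dropout?

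*Combined protocol and SAP*

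**What the plan says.** Everything relevant stands in the Sample Size section of the combined protocol and SAP.

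- Target: "Based on 80% power to detect a mean difference of 22 points between the two groups in the overall QoR 40", for which "22 subjects in each group will be needed".
- Allowance: "Allowing for a dropout rate of 20%, sample size of 54 subjects will be recruited (5 in each group").
- Result: "Therefore each treatment arm will include 27 subjects".

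The section gives no formula for the dropout inflation, does not say whether the 20% is a share of those recruited or of those needed, and cites no source for it. It also gives no standard deviation, alpha or sidedness for the 22. The bracketed 5 makes sense only as the extra women per arm: 22 + 5 = 27, and 2 × 27 = 54.

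**The concern.** A dropout rate is normally read as a fraction of those who enter the trial. On that reading the evaluable number should be divided by (1 − 0.20), which gives 28 per arm. The plan has 27, the figure that results from multiplying by (1 + 0.20), a common shortcut that always gives too few. If exactly one fifth of the recruited women were lost, the expected number left would be below the 22 that the plan says it needs.

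If the shortfall were large, the trial could reach analysis below its stated 80% power while appearing to have protected against the losses it predicted. The phrase about 5 in each group adds to the unease, because beside a total of 54 it can be misread as a group size.

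**Working it through.** **Inputs, all from the Sample Size section:** 22 evaluable per arm, 20% dropout, 54 recruited, 27 per arm, 80% power for a 22-point difference in the QoR-40. SD, alpha and sidedness are not stated, so they are assumed below and only for the power figures.

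**Step 1: reproduce the plan's figure.** 22 × (1 + 0.20) = 26.4, rounded up to 27 per arm; 2 × 27 = 54. This matches exactly. That the sponsor took this route is an inference, since no formula is shown.

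**Step 2: inflate on those recruited.** 22/(1 − 0.20) = 27.5, rounded up to 28 per arm, or 56 in all. Inflating the total instead gives 44/0.8 = 55. The plan's 54 is 1 or 2 women lower.

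**Step 3: what 27 per arm covers.**

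| Quantity | Per arm | Total |
|---|---|---|
| Expected losses at 20% | 0.2 × 27 = 5.4 | 0.2 × 54 = 10.8 |
| Spares provided | 5 | 10 |
| Expected to remain | 27 × 0.8 = 21.6 | 54 × 0.8 = 43.2 |
| Needed | 22 | 44 |
| Shortfall | 0.4 | 0.8 |

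The spares are 5/27 = 18.5% of those recruited, or 5/22 = 22.7% of those needed. The stated 20% lies between the two.

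**Step 4: effect on power.** Assume a two-sided 5% t-test (noncentral t, difference 22). Then 22 per group is the smallest size reaching 80% for SDs from 24.83 (where 21 per arm gives exactly 80%) to 25.44 (where 22 per arm does).

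| Evaluable per arm | SD 24.83 | SD 25.0 | SD 25.20 | SD 25.44 |
|---|---|---|---|---|
| 22 and 22 | 81.9% | 81.4% | 80.8% | 80.0% |
| 21.6 and 21.6 | 81.1% | 80.6% | 80.0% | 79.2% |
| 21 and 22 | 80.9% | 80.4% | 79.8% | 79.0% |
| 21 and 21 | 80.0% | 79.5% | 78.8% | 78.1% |

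At 21.6 per arm the loss against 22 is 0.7 to 0.8 of a percentage point. Power stays at or above 80% up to SD 25.20, which is (25.20 − 24.83)/(25.44 − 24.83) = 61% of the admissible band. With a one-sided 5% test instead (SD 28.18 to 28.87), power at 21.6 per arm runs from 81.0% to 79.3%.

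**The case for a change.** The best case for acting is that the inputs are all stated, the usual meaning of dropout is a share of those recruited, and on that meaning 27 per arm does not cover 20%. That the multiplication shortcut reproduces 27 explains where the figure came from but does not make it sufficient. Chance matters too: if each woman independently had a 20% chance of loss, 27 per arm would keep at least 22 in a given arm with probability P(Bin(27, 0.2) ≤ 5) = 54%, while 28 per arm would do so with probability P(Bin(28, 0.2) ≤ 6) = 68%. A corrected sentence would cost nothing, could remove the ambiguity around the bracketed 5, and could carry the missing SD and alpha.

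The arithmetic stands, and division is the better convention. The consequence does not follow. Keeping 22 is not a cliff edge: one evaluable woman fewer in each arm costs about 2 points of power (the 22-and-22 row against the 21-and-21 row). The 20% is a planning guess without a cited source, so separating it from 18.5% asks for more precision than the input has. The suggested rewording would keep 54 and only replace the assumed rate with a back-calculated tolerance. The bracketed 5 is resolved by the sentence that follows it, which gives 27 per arm. The unstated SD and alpha are a real gap in the same paragraph, because the 22 cannot be checked without them, but that is a separate point and does not turn a rounding choice into a sample-size error.

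**Conclusion.** No change follows. Read as a share of those recruited, the allowance covers 18.5% and not quite 20%, a difference of 0.4 of a woman per arm and 0.8 in total. The stated 54 is 1 or 2 below what division would give, and the nearest whole number to the expected 5.4 losses per arm is the 5 the plan provides, which leaves exactly 22.

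The headcount rests only on the plan's own numbers and on the usual reading of a dropout rate; if the 20% is taken on the 22 needed, the 5 spares exceed it. The power figures (79.2% to 81.1% at 21.6 per arm, two-sided) also rest on an assumed alpha and an SD worked back from 22 per group. Within those limits the documents do not show that 80% power is missed, and editing the sentence would gain nothing in design, analysis or interpretation.
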